Objectives: Primary: The primary objective of this study is to evaluate the natural progression of disease over time in USH1B patients using visual field testing and best corrected visual acuity. Secondary: The secondary objectives of this study are to evaluate the progression of disease over time in USH1B patients through additional assessments: 
• Microperimetry (only in selected centres)• Fundus autofluorescence (FAF)• Optical Coherence Tomography (OCT)• Full-field Electrotoretinogram (ERG),• Multifocal Electrotoretinogram,• Vision-related function and quality of life, as measured by the 25-Item National Eye Institute Visual Function Questionnaire (NEI VFQ-25)	
Rationale: This natural history study is being conducted to understand the progression of disease in USH1B patients as measured by visual acuity and visual field testing and a number of other vision-related assessments.	
Investigational product, dose, and mode of administration: N/A	
Methodology: This is a multicenter longitudinal, observational study designed to evaluate the rate of progression in USH1B subjects by visual acuity and visual field measurements and a number of other vision-related assessments.	
Inclusion and exclusion criteria: Inclusion Criteria:	

The study population consists of 50 subjects with clinical and genetic diagnosis of USH1 due to *MYO7A* mutations showing Retinitis Pigmentosa.

Male and female subjects of any ethnic group are eligible for participation in this study, providing they meet the following criteria:

1. Must be willing to adhere to protocol for long-term follow-up as evidenced by written informed consent or parental permission and subject assent.
2. Subjects diagnosed with USH1.
3. Molecular diagnosis of USH1B due to *MYO7A* mutations (homozygotes or compound heterozygotes).
4. Age eight years old or older at the time of baseline.
5. Visual acuity $\geq 20/640$ in at least one eye

Exclusion Criteria:

Subjects are excluded from the study if any of the following exclusion criteria are met:

1. Unable or unwilling to meet requirements of the study.
2. Unable to communicate with suitable verbal/auditory and/or tactile sign language (in the opinion of the investigator)
3. Participation in a clinical study with an investigational drug in the past six months.
4. Pre-existing eye conditions that would interfere with the interpretation of study endpoints (for example, glaucoma, corneal or significant lenticular opacities, cystoid macular oedema, macular hole).
5. Complicating systemic diseases in which the disease itself, or the treatment for the disease, can alter ocular function. Examples are malignancies whose treatment could affect central nervous system function (for example, radiation treatment of the orbit; leukemia with CNS/optic nerve involvement). Also excluded would be subjects with immuno- compromising diseases, as there could be susceptibility to opportunistic infection [such as cytomegalovirus (CMV) retinitis].
6. Subjects with diabetes or sickle cell disease would be excluded if they had any manifestation of advanced retinopathy (e.g. macular edema or proliferative changes).
7. Prior ocular surgery within three months.
8. Any other condition that would not allow the potential subject to complete follow-up examinations during the course of the study and, in the opinion of the investigator, makes the potential subject unsuitable for the study.

Subjects will not be excluded based on their gender, race or ethnicity.

Maximum duration of subject involvement in the study:

- Planned duration of enrollment period: 18 months
- Planned duration of assessment period: 24 months

Statistical analysis:

Continuous variables at each scheduled visit will be summarized using descriptive statistics (n, mean, quartiles, standard deviation, minimum and maximum). For categorical variables, tabular summaries will consist of presenting the number and percentage in each category, including missing category, if applicable. The annual rate of progression of each endpoint will be estimated by means of regression models for the analysis of longitudinal data, as appropriate.

Table 1: Study Schedule of Events

Evaluation ^a	Baseline	1 year follow-up	2 year follow-up
Informed Consent ^b	•		
Eligibility Criteria	•		
Demographics	•		
Medical History/Review of Systems ^c	•		
NEI VFQ-25=25-Item National Eye Institute Visual Functioning Questionnaire ^d	•	•	•
Concurrent Medical Conditions \ Disease progression	•	•	•
Pregnancy or nursing status	•	•	•
Medication/Nutritional Supplements/Therapies/Procedures	•	•	•
Ophthalmic examination ^e	•	•	•
Refraction and Best corrected visual acuity	•	•	•
Visual Field Assessments (Kinetic and Static)	•	•	•
Microperimetry	•	•	•
Fundus Photography*	•	•	•
Fundus autofluorescence*	•	•	•
Optical Coherence Tomography*	•	•	•
Multifocal electroretinogram ^f **	•	•	•
Full field electroretinogram ^g **	•	•	•

Notes:

- a It may take approximately 2 days to complete all required assessments.
- b Informed consent will be obtained
- c Includes family history, vision-related medical history, vision-related family history and abstracting of all previous available tests and examination.
- d The NEI VFQ-25 will be administered at the start of the scheduled visit so that any interaction between physician and subject will not influence the subject's responses to the questionnaires.
- e Clinical ophthalmic examination will include slit lamp examination, direct and/or indirect ophthalmoscopy, and cataract grading.
- f To be performed only in patients with stable fixation
- g If a patient has a non-detectable ERG response at previous visit, ERG assessments will not be performed at subsequent study visits.
- * to be performed without dilation in pregnant subjects
- ** to be not performed in pregnant subjects

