2 STUDY OBJECTIVES AND PURPOSE

2.1 Rationale for the Study

Drug development in non-syndromic and syndromic RP has proved to be challenging, also due to the difficulty in applying endpoints commonly used in ophthalmology clinical trials. For instance, BCVA, which is used as a registration endpoint in many ophthalmologic clinical trials, may be not a viable endpoint for use in this slowly progressing disease. In addition, due to the slow progression of RP and the large amount of variability inherent to visual function assessments, some assessments have insufficient sensitivity for quantifying clinically meaningful changes in photoreceptor loss in a time frame desirable for clinical trials.

This natural history study (NHS) is being conducted to understand the progression of disease in USH1B patients as measured by a number of vision-related assessments. Disease progression will be evaluated as change over time in these measures, and associations between the endpoints will be examined.

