7.1.2 Baseline visit

The following procedures will be performed:

- Obtaining written IC (and assent if applicable) by subject, and/or the subject's parent(s) or legally authorized guardian(s)
- Assessment of eligibility according to the inclusion/exclusion criteria
- Collection of medical history, including subject's ocular history, previous medications, and previous test and examination
- NEI VFQ-25 plus its additional items
- Concurrent Medical Conditions
- Pregnancy or nursing status
- Concomitant treatment (medications/nutritional supplements/therapies/procedures)
- Refraction and BCVA
- Visual field assessments (kinetic and static)
- Clinical ophthalmic examination
- Microperimetry
- Fundus Photography
- Fundus autofluorescence
- Optical Coherence Tomography
- Confirmation of eligibility according to the inclusion/exclusion criteria
- Multifocal electroretinogram
- Full field electroretinogram

7.1.3 1 year and 2 year follow-up visit

The following procedures will be performed:

- NEI VFQ-25 plus its additional items
- Concurrent Medical Conditions \ Disease progression
- Pregnancy or nursing status
- Concomitant treatment (medications/nutritional supplements/therapies/procedures)
- Refraction and BCVA
- Visual field assessments (kinetic and static)

- Clinical ophthalmic examination
- Microperimetry
- Fundus Photography
- Fundus autofluorescence
- Optical Coherence Tomography
- Multifocal electroretinogram
- Full field electroretinogram

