7.2.2.9 Electroretinography

Full field electroretinograms will be performed in both eyes using a Reticom (Roland Consultant) or Espion D15 (Diagnosis) equipment according to the International Society for Clinical Electrophysiology of Vision standards(McCulloch, Marmor et al. 2015). Scotopic and photopic assessments will be performed as follows:

- Dark-adapted (40 minutes)
- Rod response (0.01 ERG)
- Maximal combined rod/cone response (3 ERG)
- Light-adapted (10 minutes)
- Cone response (3 ERG)
- Response to flicker (30 Hz flicker ERG)

Details are provided in the Technical Manual of Procedures.

If a patient has a non-detectable ERG response to all stimuli at previous visit (or as assessed by medical history), ERG assessments will not be performed at subsequent study visits.

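### Table 1 note g and section 7.2.2.9 give different rules for stopping full-field ERG, and section 8.2 does not say how a non-detectable or skipped ERG is analysed; if left missing, unpaired visit means understate ERG decline

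*Combined protocol and SAP*

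**What the plan says.** Progression on full-field ERG is a secondary objective (section 2.2.2). Section 2.1 sets the frame: "Disease progression will be evaluated as change over time in these measures".

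Two passages say when ERG testing stops.

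- Table 1, note g: "If a patient has a non-detectable ERG response at previous visit, ERG assessments will not be performed at subsequent study visits". It names no stimulus and gives no history route.
- Section 7.2.2.9 stops testing at later visits for a patient with a "non-detectable ERG response to all stimuli at previous visit (or as assessed by medical history"). The same section lists four recorded responses: rod, combined, cone and flicker.

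Table 1 and section 7.1.2 list "Full field electroretinogram" at baseline with no exemption for history.

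ERGs can also be missing for other reasons. The double-asterisk note to Table 1 marks both ERG tests "to be not performed in pregnant subjects", and section 4.3 drops assessments that need eye drops in pregnant and nursing patients. "Pregnancy or nursing status" is recorded at all three visits.

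Section 8.2 gives descriptive statistics at each visit and an annual rate from longitudinal regression whose form is left open. Its only words on missing data concern a category for categorical variables. Section 8.5 analyses all progression data in the Enrolled Set and adds no ERG rule.

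**The concern.** There are two linked problems.

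The first is in the text. A patient with one absent response and three measurable ones is retested under section 7.2.2.9. Under a literal reading of note g that patient may be stopped. A patient known only from history to have no response is covered by section 7.2.2.9 alone, and it is unclear whether that patient has a baseline ERG. An ERG not done because a site followed the other passage cannot be recovered at analysis.

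The second is in the analysis, and it exists under either rule. Later testing depends on the patient's own earlier result, and nothing says what value a non-detectable or skipped ERG takes. If these results drop out, the later visit means come from patients with better-preserved responses. ERG would then seem to change less than it does, in a study meant to learn which measures can track this disease. The n at each visit would show a shrinking denominator, but not the reason.

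**Working it through.** The plan states no ERG figure and no formal sample size calculation, so there is nothing to reproduce. What can be checked is the direction of the bias and, under assumptions, its rough size.

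**Assumed inputs (none from the documents).** One response per patient; log-normal amplitude; log-SD 1.2 between patients; measurement log-SD 0.25; detection limit 2 uV; median 6 uV (range 4 to 10); decline 10% a year (range 5 to 15%); ERG at years 0, 1 and 2.

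**Step 1. True change.** 0.9² − 1 = −19.0%.

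**Step 2. Non-detectable results blank, everyone retested.** Total log-SD s = √(1.2² + 0.25²) = 1.2258. For median m, the overall mean is M = m·exp(s²/2). With a = (ln 2 − ln m)/s, the detectable fraction is Φ(−a), and the mean among detectable patients is M·Φ(s−a)/Φ(−a).

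- Baseline, m = 6: M = 12.718, a = −0.896, so 12.718 × 0.9831/0.8149 = 15.34.
- Year 2, m = 6 × 0.81 = 4.86: M = 10.301, a = −0.724, so 10.301 × 0.9744/0.7656 = 13.11.
- Apparent change: 13.11/15.34 − 1 = −14.5%.

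**Step 3. Add the stopping rule.** Selection on earlier noisy results needs simulation (1,000,000 patients per run).

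| Handling | Baseline mean | Year 2 mean | Change |
|---|---|---|---|
| Truth | 12.72 | 10.30 | −19.0% |
| Non-detectable and skipped both blank | 15.34 | 13.55 | −11.7% |
| Tested non-detectable = 0, skipped missing | 12.50 | 12.94 | +3.5% |

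With both blank, 19.0 − 11.7 = 7.3 points are missed. Blanking accounts for 19.0 − 14.5 = 4.5 of them and the stopping rule for 14.5 − 11.7 = 2.8. Over the nine combinations of median and decline, blanking costs 1.3 to 8.9 points and stopping 1.3 to 5.3.

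A separate set of 56 scenarios (10 to 70% non-detectable at baseline, proportional or fixed decline) gave a smaller percentage fall, or a rise, under both codings every time. The statement holds for percentage change. On the absolute scale, a few fixed-decline scenarios with many non-detectable patients showed a larger fall than in the whole cohort.

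**Step 4. How much the wording conflict could matter.** Step 3 stops on the same response that is summarised. With four responses (equal medians 6 uV, correlation 0.7, 10% a year), stopping only when all are absent leaves 47 of 50 patients tested at year 2 (40 to 50 over eight sets of medians and correlations 0.5 to 0.9). Stopping then adds only 0.3 points to the effect of blanking (0 to 1.3), and either coding shows about −14% against −19%, so there is no apparent rise. If note g meant any one absent response, 28 of 50 would still be tested (14 to 40), and stopping would shift the visit mean by 20 points (5 to 56). That second set of figures depends wholly on that reading.

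**Step 5. Is there a safe floor?** Non-detectable and skipped results are kept at a fixed value; decline is 10% a year and the truth −19.0%.

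| Log-SD, median (uV) | Zero | Half limit | Limit | Paired change |
|---|---|---|---|---|
| 1.2, 6 | −20.4% | −19.5% | −18.6% | −19.0% |
| 0.7, 3 | −28.8% | −22.3% | −16.6% | −18.1% |
| 0.5, 3 | −33.1% | −24.5% | −17.1% | −17.5% |
| 0.7, 2 | −37.1% | −22.7% | −13.1% | −17.5% |
| 0.5, 2 | −47.9% | −26.0% | −12.3% | −16.3% |

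No floor is accurate throughout, and paired change drifts as well.

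**Step 6. Regression rate.** With blanks, a random-intercept model overstated decline by 25% on raw amplitude (10 to 44%) and understated it by 8% on log amplitude (4 to 13%). At 50 patients and log-SD 1.2, a left-censored random-intercept model converged in all 300 trials of each of nine scenarios. In the main case its mean log slope was −0.105 a year (truth ln 0.9 = −0.105), against −0.097 with blanks and −0.101 for paired change. The spread across trials was 0.026 to 0.032, so the bias with blanks is modest beside sampling error.

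**The case against.** Note g is a table footnote and section 7.2.2.9 is the full procedure, so the footnote is most naturally read as shorthand. On that reading stopping alone adds almost nothing (step 4). The Technical Manual of Procedures, which is not available here, may define a non-detectable response. No passage says these results will be left missing. The annual rate is to come from regression, not from comparing visit means, and the visit tables report n. ERG is a secondary measure in an observational study with no formal sample size calculation.

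Much of this stands, and it limits the size of the point. It does not remove it. No text says which passage governs, and the shorthand reading does not settle whether history removes the baseline ERG. This also matters for analysis: section 7.2.1.2 collects earlier results, but section 8.2 reserves retrospective data for a secondary analysis, so a patient exempted at baseline might have no ERG value in the main one. A definition in the manual would not by itself supply an analysis rule; no passage assigns one to it.

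A reader might infer more than the documents support:

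- That nearly half the later ERGs will be lost. This needs the any-one-stimulus reading of note g, which the text permits but does not state.
- That the annual ERG rate will be understated. The direction depends on a model and scale that the plan leaves open.
- That the plan intends to drop these results. It is silent.

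**Conclusion.** The point holds as an internal inconsistency together with an unspecified analysis rule, and it should be corrected. Confidence is high in the textual difference and in the gap in section 8.2. It is also high in the direction of bias in the percentage change of unpaired visit means if skipped or non-detectable results are left missing.

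The size is illustrative only. Under the assumed amplitudes for a single response, a true −19% appears as about −12% or about +3.5%, depending on coding. With four responses and stopping only when all are absent, it appears as about −14%. The apparent rise therefore depends on how closely stopping follows the response being summarised. The primary BCVA and visual field endpoints are not affected.

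**What to change.** (a) Reconcile note g and section 7.2.2.9 into one rule, used in both places, and say whether the history clause applies to the baseline ERG.

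(b) Add one CRF code, *non-detectable, not retested*, for each ERG skipped under the rule. Keep it distinct from ERGs omitted for pregnancy or nursing, using the status already collected at each visit, and from those missing for other reasons.

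(c) In section 8.2, keep non-detectable and skipped results in the visit summaries at a floor fixed in advance. Repeat the summaries at other floors (zero, half the detection limit, the limit), because no single floor is accurate across plausible amplitude distributions. Report the percentage non-detectable over all subjects at each visit.

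(d) For the annual rate, treat tested non-detectable results as left-censored on log amplitude and leave later skipped visits out of the likelihood, or prespecify a comparable method. Both eyes are recorded, so include a patient-level random effect. Report paired within-patient change alongside, noting that it covers only patients still detectable.

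The cost is the wording of one rule, one CRF code and slightly more analysis for one secondary endpoint. Parts (b) to (d) need no extra tests.

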1 BACKGROUND INFORMATION

1.1 Indication and Current Treatment Options

With an overall prevalence of 1 in 6000 (Kimberling, Hildebrand et al. 2010), the autosomal recessive Usher syndrome (USH) is the most common combination of genetic deafness and blindness due to Retinitis Pigmentosa (RP) (Gregory-Evans, Pennesi et al. 2013). USH type I which accounts for approximately 40% of all USH cases (Rosenberg, Haim et al. 1997) is the most severe form with the RP onset in childhood (Gregory-Evans, Pennesi et al. 2013). USH type IB (USHIB) accounts for 35-50% of USH [(Ouyang, Yan et al. 2005), 1 in 30-42000 individuals] and is caused by mutations in *MYO7A*. While hearing loss in USH can be counteracted by cochlear implantation, RP remains untreatable.

2 STUDY OBJECTIVES AND PURPOSE

2.1 Rationale for the Study

Drug development in non-syndromic and syndromic RP has proved to be challenging, also due to the difficulty in applying endpoints commonly used in ophthalmology clinical trials. For instance, BCVA, which is used as a registration endpoint in many ophthalmologic clinical trials, may be not a viable endpoint for use in this slowly progressing disease. In addition, due to the slow progression of RP and the large amount of variability inherent to visual function assessments, some assessments have insufficient sensitivity for quantifying clinically meaningful changes in photoreceptor loss in a time frame desirable for clinical trials.

This natural history study (NHS) is being conducted to understand the progression of disease in USH1B patients as measured by a number of vision-related assessments. Disease progression will be evaluated as change over time in these measures, and associations between the endpoints will be examined.

2.2 Study Objectives

2.2.1 Primary Objectives

The primary objective of this study is to evaluate the natural progression of disease over time in USHIB patients using best corrected visual acuity and visual field testing.

2.2.2 Secondary Objectives

The secondary objectives of this study are to evaluate the progression of disease over time in USHIB patients through additional assessments:

- Microperimetry (only in selected centres)
- Fundus autofluorescence (FAF)
- Optical Coherence Tomography (OCT)
- Full-field Electrotoretinogram (ERG),
- Multifocal Electrotoretinogram,
- Vision-related function and quality of life, as measured by the 25-Item National Eye Institute Visual Function Questionnaire (NEI VFQ-25).

3 STUDY DESIGN

3.1 Study Design

This is a multicentre longitudinal, observational study designed to evaluate disease progression in subjects with USH1B by several vision-related assessments.

After informed consent (and assent, if applicable) is obtained from the subject or his/her parent(s) or legally authorized guardian(s), initial eligibility will be based on a confirmed clinical and molecular diagnosis of USH1B.

Subjects will be assessed using the following schedule:

- Baseline visit
- 1 year follow-up visit
- 2 year follow-up visit

This is an observational study; no treatment for USH1B with an investigational medicinal product will be provided. Subjects who are eligible to enroll into this study are not obligated to participate. Once enrolled, subjects may withdraw at any time and for any reason without prejudice to any future medical care or research opportunities. A subject's participation in this observational study does not guarantee participation in future interventional studies.

The evaluation performed in the course of this study are part of the standard clinical care of USH1B patients. The study does not require any additional test or administration of any drugs.

3.2 Duration and Study Completion Definition

The subject's maximum duration of participation is expected to be approximately 24 months. Recruitment period is 18 months.

The study will be completed in approximately 3.5 years.

The Study Completion Date is defined as the date the final subject, across all sites, completes their final protocol-defined assessment. The Study Completion Date is used to ascertain timing for posting and reporting of study results.

3.3 Sites and Regions

The study is planned to be conducted at 3 sites: the Eye Clinic of the University of Campania Luigi Vanvitelli, Naples, Italy, as Coordinating Centre, the Instituto de Investigacion Sanitaria de la Fundacion Jimenez Diaz, Madrid, Spain and the Stichting Oogziekenhuis Rotterdam, Rotterdam, The Netherland.

4 STUDY POPULATION

It is expected that approximately 50 patients may be recruited into the study during the recruitment period.

Each subject must participate in the informed consent process and provide written informed consent/assent before any procedures specified in the protocol are performed.

4.1 Inclusion Criteria

Male and female subjects of any ethnic group are eligible for participation in this study, providing they meet the following criteria:

1. Must be willing to adhere to protocol for long-term follow-up as evidenced by written informed consent or parental permission and subject assent.
2. Subjects diagnosed with USH1.
3. Molecular diagnosis of USH1B due to *MYO7A* mutations (homozygotes or compound heterozygotes).
4. Age eight years old or older at the time of baseline.
5. Visual acuity $\geq 20/640$ in at least one eye

